11.3 Final Analysis Plan

The primary analysis will be descriptive in nature. For every item on the survey, we will calculate descriptive statistics in the form of frequencies and relative frequencies for categorical variables and means, medians, and standard deviations for continuous variables. We will also calculate the margin of error for each item based on 95% confidence intervals. The items on the survey focus on the following research question domains:

- 1. What is the frequency of screening, counseling, and referral for each substance category?
- 2. Who is primarily responsible for screening and counseling in practice?
- 3. What barriers to screening practices are most commonly identified for each substance type?
- 4. What facilitators of screening practices implementation are the most endorsed?
- 5. What is dentists' willingness to engage with point of care interventions (naloxone, NRT)?
- 6. What is the extent of prior training and willingness to engage in future training?

For the first 4 questions, we will report responses germane to adolescent and adult patients separately.

Secondary Objectives: This study has two secondary objectives. Analysis plans for each objective are detailed below:

(1) Determine whether practitioner and practice characteristics are associated with implementation of screening, counseling, and referral.

To determine whether practitioner characteristics (including age, sex, and race) and practice characteristics (including setting, practice scope, practice region, practice patient age, practice patient race, and number of patients per week) are related to items focusing on screening, counseling, and referral, we will use Fisher's Exact Test for nominal variables and Spearman and Pearson correlations for ordinal and interval/ratio level variables, respectively. Given the large number of items, we will also consider whether items can be summarized using scores based on data reduction techniques such as principal components analysis or principal-axis factor analysis. If the data do not support the use of summary scores, we will use the Benjamini–Hochberg procedure to adjust for the false discovery rate of the p-values resulting from multiple testing.

(2) Determine whether there are differences between adults and adolescents on the extent to which substance use is perceived as problematic.

We will use paired-sample t-tests to account for the same participant providing both ratings on the adolescents and adults and to test whether there is a difference on the degree to which tobacco/nicotine, alcohol, cannabis, and illicit drug use is problematic. Given that the outcomes are rated on an ordinal scale, we will also perform a sensitivity analysis using the Wilcoxon Signed Rank test.

Exploratory Objective: Are there profiles of screening behaviors across the four substance categories?

To determine whether there are profiles among the screening behaviors across the four substance use categories, we will use hierarchical cluster analysis. We will choose the optimal linkage/method and similarity/distance measure based on the characteristics of the data. We will select the number of clusters based on the examination of the agglomeration schedule, selecting a range of solutions for further inspection based on the magnitude of dissimilar clusters being combined. We will then compare these profiles, both on the levels of screening behaviors that were inputs into the analysis as well as practitioner and practice characteristics that were external to the formation of the clusters. Selection of the final solution will be based on maintaining both interpretability and parsimony. This analysis will be performed separately for adolescents and adults.

Note that all analyses assume independence of observations by ignoring the clustering effect of providers nested within clinics. The degree to which any inferential analyses are

Document Owner: SUDS Study PI & Study Manager

valid will be dependent on the size of the intraclass correlation and the number of dentists that belong to the same clinic.

Missing Data. Data from incomplete questionnaires may be included in data analyses. Depending on the extent of missing data and available resources for analyses, the study team may consider statistically appropriate methods for imputing missing information. If the proportion of missing data is very small, we will rely on case-wise analysis.

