Subsequently, Parish and colleagues¹⁰¹ conducted a nationally representative (n=1802; 71% response rate) survey of US dentists using a sampling frame from the ADA Survey Center assessing the relationship between their practice, knowledge, behaviors, and attitudes with their query about substance misuse and their belief that such screening is part of their professional role. Approximately three-quarters of dentists reported asking their patients about substance misuse on their patient health history form; however, approximately two-thirds did not agree that such screening was compatible with their professional role. More than one-third of respondents had no prior training in substance misuse and self-reported clinical knowledge regarding illicit drug use was low, with more than 20% endorsing "none/limited" knowledge in this area. Prior training regarding substance misuse was positively associated with dentists' viewing such screening as compatible with their professional role.

[name] and colleagues¹⁰²⁻¹⁰⁴ surveyed practicing dentist members of the National Dental Practice Based Research Network (Network; N=822; 58% response rate) regarding pain management prescribing practices and risk mitigation implementation, including implementation of screening for substance use broadly. Most dentists reported including assessment of current tobacco use (94%), current alcohol use (75%), and current illicit drug use (69%). However, only slightly more than half (52%) reported assessing patients for current prescription drug abuse and/or history of substance abuse treatment.¹⁰² Further, nearly half of respondents reported having never accessed their state prescription drug monitoring program.¹⁰³ Higher frequency of assessing for substance misuse and abuse was associated with more conservative opioid prescribing practices.¹⁰² Training related to identification and assessment of drug abuse/addiction (48%) or identification of prescription drug diversion (25%) was uncommon, though more prevalent among recent dental school graduates. Training experiences were associated with prescribing practices including greater frequency of providing patient education and higher frequency of drug monitoring program use.¹⁰⁴

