6 STUDY SCHEDULE

6.1 Phase 1, Part A – Recruitment of Practitioners into the Study

- Eligible dentists will be identified from responses to the Network Enrollment Questionnaire and will be invited to participate based on inclusion criteria.
- A stratified random sample will be taken. The sample will be stratified based on regional membership to ensure representation of practitioners across the US. To provide adequate representation of practitioners working with adolescent patients, pediatric dentists will be oversampled.
- Agreement to complete the questionnaire will indicate that study participants have read the consent information, and this will imply tacit consent. A waiver of signed consent will be requested from the IRB.

Phase 2, Part B- Retest of the Questionnaire

- Dentists selected from among those study participants who completed the questionnaire will be emailed a second online questionnaire request approximately two weeks after the receipt of their first completed questionnaire.
- Dentists will be sampled for the retest until n=50 retest completions are achieved.
- Completion of the retest questionnaire will indicate implied consent.

6.2 Phase 2, Merging Study Questionnaire with Enrollment Questionnaire and Completion of Data Analyses

- Study questionnaire and Network enrollment questionnaire data will be linked using participant IDs.
- Contact information will be removed from the final merged dataset and data will be stored/saved using Unique Participant IDs.
- Data Analyses will be completed as described in Section 11.3 Final Analysis Plan.

Document Owner: SUDS Study PI & Study Manager

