11.2 Sample Size Considerations

Given that the primary analysis is descriptive, the power analysis was based on generating 95% confidence interval widths (i.e., margin of error typically reported with survey and polls) with 80% power. With a sample size of 825 participants, means will have 95% confidence interval widths of .136 standard deviation units (i.e., ±.068 standard deviation units around the mean). Because confidence interval widths for proportions are dependent on the value of the proportions, we estimated the widths for proportions of 0.10, 0.25, 0.50, 0.75, and 0.90. These estimates are listed in the table below:

Proportion	95% Confidence Interval		
.100	.080	.123	
.250	.221	.281	
.500	.465	.535	
.750	.719	.779	
.900	.877	.920	

All power analyses were carried out using PASS 2023.¹⁰⁷

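### Section 11.3 reports unweighted percentages with sampling-only margins of error and makes no use of nonresponders' enrollment data, although these are held for every invited dentist

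*Protocol*

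**What the plan says.** Section 11.3 fixes the primary estimator: "we will calculate descriptive statistics in the form of frequencies and relative frequencies for categorical variables", with means, medians and standard deviations for continuous items. It then states: "We will also calculate the margin of error for each item based on 95% confidence intervals". No weights are named. Section 11.2 derives the expected precision from the target number of respondents: "With a sample size of 825 participants, means will have 95% confidence interval widths of .136 standard deviation units".

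Completing or updating an Enrollment Questionnaire in cycle 3 is an inclusion criterion (section 5.1), and section 6.1 draws the frame from it: "Eligible dentists will be identified from responses to the Network Enrollment Questionnaire". Section 6.2 then says: "Study questionnaire and Network enrollment questionnaire data will be linked using participant IDs". That linkage covers only dentists who returned a study questionnaire. The Protocol Summary describes the same pairing, made to see whether implementation gaps vary by practice and practitioner characteristics.

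The missing-data paragraph of section 11.3 concerns incomplete questionnaires. Under section 7, nonresponders receive reminders and Node Coordinator contact, are then taken to be not interested, and the survey closes at 825 completions. Neither the number to be invited nor an expected response rate is given.

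**The concern.** The main product of this study is a list of percentages with margins of error, presented as describing Network dentists. A margin computed from n = 825 covers the chance of drawing one sample rather than another. It does not cover the possibility that dentists who complete a 25-30 minute questionnaire differ from those who do not.

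The protocol's own background gives reason to expect that some enrollment characteristics track the outcomes. In the regional Network survey, each 10% increase in the share of patients aged 18 or younger went with a 20% lower likelihood of each further step of tobacco risk assessment. In the earlier national Network survey, addiction training was more common among recent graduates. If response varies with such characteristics, unweighted percentages shift, and the information needed to detect and partly correct the shift is already held. Section 11.3 adds a caveat about clustering of dentists within clinics but none about unit nonresponse.

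**Working it through.** **Inputs from the protocol.** n = 825 and 95% intervals (section 11.2); planning proportions .10 to .90 (section 11.2). The background section gives response rates for four earlier dentist surveys: 58% ("Network; N=822; 58% response rate"), 68% (a former dental practice network), 71% (a national survey) and 72% (a regional Network survey). These serve as proxies because no rate is stated for this study.

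**Assumed.** The responder-minus-nonresponder gap *d* is not in the documents. Values of 5 and 10 points are used for illustration.

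**Step 1: the plan's own figures.** For means, 1.96/√825 = .068 SD, width .136, as stated. Exact (Clopper-Pearson) limits at n = 825 are .0804-.1225, .2208-.2810, .4653-.5347, .7190-.7792 and .8775-.9196. They agree with the section 11.2 table to within .001. The stated precision therefore reproduces, and it treats the 825 as a simple random sample with full response.

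**Step 2: margin used for comparison.** Wald half-width = 1.96 × √(p(1−p)/825):
- p = .50: 3.4 points
- p = .25 or .75: 3.0 points
- p = .10 or .90: 2.05 points

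**Step 3: gap at which bias equals the margin.** Bias = (1 − response rate) × *d*, so the break-even gap is the half-width divided by (1 − response rate). At 58% and p = .50 this is 3.41/.42 = 8.1 points.

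| Response rate | p = .10 or .90 | p = .25 or .75 | p = .50 |
|---|---|---|---|
| 58% | 4.9 | 7.0 | 8.1 |
| 68% | 6.4 | 9.2 | 10.7 |
| 71% | 7.1 | 10.2 | 11.8 |
| 72% | 7.3 | 10.6 | 12.2 |

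**Step 4: coverage of the nominal 95% interval.** Coverage = Φ(1.96 − b/se) − Φ(−1.96 − b/se), with b the bias and se = √(p(1−p)/825). At p = .50:
- *d* = 5, 58% response: bias .42 × 5 = 2.1 points, coverage 77%
- *d* = 5, 72% response: bias .28 × 5 = 1.4 points, coverage 87%
- *d* = 10, 58% response: bias 4.2 points, coverage 33%
- *d* = 10, 72% response: bias 2.8 points, coverage 64%

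At p = .10, a 5-point gap at 58% response gives a bias of 2.1 points against a 2.05-point margin, and coverage of about 48%.

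**Step 5: what weighting could recover.** Take two equal cells with response 70% and 46% (58% overall) and prevalence .60 and .40, all assumed. The unweighted estimate is (.70 × .60 + .46 × .40)/1.16 = .521 against a true .500. Weights remove these 2.1 points at a design effect of 1.045. If both contrasts are halved (64% and 52%; .55 and .45), the unweighted estimate is .586/1.16 = .505, so only about 0.5 points are there to remove.

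**Step 6: precision cost.** With a weight CV of 0.3, the design effect is 1 + 0.3² = 1.09, and 3.41 × √1.09 = 3.56, about ±3.6 points.

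**The case against.** The strongest reply is that weighting and responder comparisons are commonly left to an analysis plan, which is not shown, and that section 15.3 leaves report content to a Statistical Analysis Standard Operating Procedure. This stands in part: a later document could add the adjustment. However, section 11.3 is titled the final analysis plan and fixes unadjusted estimators. Section 6.2 is a data-flow decision that covers participants only. Under section 14.3, consent is given by entering the questionnaire, so nonresponders give none. Use of their records is best stated in the protocol.

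A margin of error is by definition a sampling quantity, and the protocol does not claim that it covers more. That is correct. The point is the missing companion analysis and caveat, not a false statement.

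Nor is nonresponse ignored. There are reminders, coordinator contact, a $50 payment and regional quotas. These may reduce it, but they correct no estimate beyond the regional balance.

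A reader might infer that bias probably exceeds the margins, or that it inflates screening figures. The documents support neither, because they give no gap and no direction. The 58% rate is the lowest of the four reported. Of the four scenarios at p = .50 above, only 58% response with a 10-point gap passes the margin.

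Finally, the protocol does not list the fields of the Enrollment Questionnaire, and section 12 names only selected enrollment data as a source. Region and specialty are clearly known for the frame. Age, sex, setting and patient mix are a reasonable inference.

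**Conclusion.** The point holds in a limited form. The plan reports unweighted percentages with sampling-only margins and leaves unused the enrollment data held for nonresponders. Whether this matters numerically cannot be settled from the protocol. At p = .50, bias passes the ±3.4-point margin only if the gap is above about 8 points at 58% response, or about 11-12 points at 68-72%. At p = .10 or .90 the thresholds are about 5 points and about 6-7 points. Below them the bias stays inside the margin, but coverage still falls below 95%. These figures rest on proxy response rates and assumed gaps. It would also be wrong to read weighting as a cure: enrollment variables do not measure interest in substance use, and the share of any bias that they explain is unknown. The change is still worth making, because it uses data already held and costs little precision.

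**What to change.** - In sections 6.2 and 11.3, state that the enrollment variables of all invited dentists are kept for nonresponse analysis.
- Report the response rate among those invited, and compare responders with nonresponders on the enrollment variables available, such as region, specialty, setting, age, sex and patient age mix.
- For domains 1-6, report nonresponse-weighted estimates (response propensity, or raking to the invited eligible frame) as a sensitivity analysis beside the unweighted ones, with intervals that reflect the weights.
- State that the unweighted margins cover sampling error only, and that weighting removes only bias explained by enrollment variables.

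The cost is slightly wider intervals in the weighted analysis (the ±3.6 points above), some analysis time, and possibly short IRB wording on the use of nonresponders' enrollment records.

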3 OBJECTIVES AND OUTCOME MEASURES

3.1 Primary

Objective	Brief Description/Justification of Outcome Measure	Outcome Measured By	Time Frame
The primary objective of this study is to conduct a national survey of dentists to assess knowledge, attitudes, and behaviors related to substance use screening implementation among adolescent, young adult, and adult dental patients.	Although dentists regularly encounter patients with problematic substance use and recognize the importance of screening for substance abuse, they have limited exposure to addictions training and generally lack systems to aid in screening, intervention, and referral to addictions treatment. Self-reported knowledge (prior training experiences), attitudes, and current behaviors regarding screening implementation are critical to understand in guiding development of future training and implementation initiatives.	The primary outcome measures will be assessed by an electronic questionnaire regarding current perspectives and practice behavior related to substance use screening among patients. Specific items (or groups of items) will assess each domain with either dichotomous, Likert scale, frequency, or percentage ratings.	Administration of an electronic questionnaire will be used to measure this outcome.

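### For secondary objective 1 the only test named for a nominal characteristic is Fisher's Exact Test, which ignores response order when the item is an ordered rating

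*Protocol*

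**What the plan says.** Protocol section 11.3 states secondary objective 1 as: "Determine whether practitioner and practice characteristics are associated with implementation of screening, counseling, and referral". Three of the named factors describe the dentist: age, sex and race. Six others describe where the dentist works, listed as "practice characteristics (including setting, practice scope, practice region, practice patient age, practice patient race, and number of patients per week"). To relate them to the items, "we will use Fisher's Exact Test for nominal variables and Spearman and Pearson correlations for ordinal and interval/ratio level variables, respectively". The section adds that summary scores from principal components or factor analysis will be considered, with Benjamini-Hochberg adjustment if such scores are not supported.

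On response formats, section 3.1 says: "Specific items (or groups of items) will assess each domain with either dichotomous, Likert scale, frequency, or percentage ratings". The first research question in section 11.3 concerns how frequently screening, counseling and referral occur.

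For secondary objective 2, section 11.3 recognises that its outcomes are ordinal and adds a Wilcoxon signed rank test as a sensitivity analysis.

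Section 6.2 says the analyses will be completed as section 11.3 describes.

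**The concern.** The rule assigns a method by measurement level but does not say whose level: the characteristic's, the item's, or that of both. Five of the nine named characteristics (sex, race, setting, scope, region) would normally be nominal. Pairing one of them with an ordered rating is therefore a regular case under this objective, and the rule does not handle it well on any reading:

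- **The level is that of the characteristic.** Fisher's Exact Test is applied to a table with ordered columns and treats the response levels as unordered labels.
- **The level is that of both variables.** Fisher's Exact Test covers nominal-by-nominal pairs only, and nominal-by-ordered pairs have no test.
- **The level is that of the item.** A Spearman or Pearson correlation would be computed against region or race, which have no order.

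Nor is a test named for a nominal characteristic against a summary score.

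What is at stake is sensitivity. If one group of dentists screens more often than another in a consistent direction, a test that ignores the order spreads its power over patterns that are not of interest and misses the difference more often than it needs to.

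**Working it through.** **Step 1: the plan's own figures.** Section 11.2 says "the power analysis was based on generating 95% confidence interval widths", and "With a sample size of 825 participants, means will have 95% confidence interval widths of .136 standard deviation units". The half-width is 1.96/√825 = 0.0682 SD, so the width is about 0.136 SD, as stated. Exact Clopper-Pearson limits at n=825 reproduce all five stated intervals for proportions (for example .465 to .535 at .50). The precision statement is sound, but it gives no effect size or power target for the association tests, so every effect below is an assumption.

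**Step 2: two groups, 65/35.** From the protocol: n=825. Assumed: groups of 536 and 289 (0.65 × 825 = 536.25; 0.35 × 825 = 288.75); a 5-level item with base probabilities .15/.20/.25/.20/.20; a proportional-odds shift, in which the logit of each cumulative probability moves by log(OR); two-sided 5%; 2,000 simulated surveys per odds ratio. The table test is chi-square on the 2×5 table, as a large-sample stand-in for Fisher's Exact Test. The rank test is Wilcoxon-Mann-Whitney.

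| Odds ratio | Table test | Rank test | Loss (points) |
|---|---|---|---|
| 1.3 | 33% | 52% | 52 − 33 = 19 |
| 1.4 | 52% | 73% | 73 − 52 = 21 |
| 1.5 | 70% | 87% | 87 − 70 = 17 |

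With no effect, the rejection rates are 4.5% and 4.7%, so the gap does not come from a difference in size.

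**Step 3: other layouts.** Same method, base probabilities .10/.20/.25/.25/.20, 4,000 simulations each, with Kruskal-Wallis as the rank test.

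| Layout (assumed) | Odds ratio | Table test | Rank test |
|---|---|---|---|
| Two groups, 550/275 | 1.3 | 31% | 51% |
| Two groups, 550/275 | 1.4 | 50% | 72% |
| Two groups, 550/275 | 1.5 | 69% | 86% |
| 50 pediatric vs 775 others | 1.5 | 18% | 34% |
| 50 pediatric vs 775 others | 2.0 | 53% | 77% |
| 50 pediatric vs 775 others | 2.5 | 80% | 94% |
| Six equal groups, graded | 1.75 (extremes) | 38% | 64% |
| Six equal groups, graded | 2.0 (extremes) | 59% | 85% |

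The figure of 50 is the protocol's minimum number of pediatric dentists. The six groups are an assumption. Null rejection is 4% to 5% for both tests.

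**Step 4: is chi-square a fair stand-in?** Monte Carlo Fisher-Freeman-Halton tests were run on three of these scenarios. Power was 53% (550/275, OR 1.4), 51% (50/775, OR 2.0) and 39% (six groups, OR 1.75), against 50%, 53% and 38% for chi-square. The two agree within about 3 points.

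**Step 5: where the advantage disappears.** On a dichotomous item there is no order to ignore, so Fisher's Exact Test loses nothing on that account. For one non-monotone pattern that was simulated, the table test had 61% power and the rank test about 5%. The advantage in steps 2 and 3 therefore belongs to consistent shifts in one direction.

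**The case against.** **The power loss is conditional.** A proportional-odds shift is the kind of alternative that suits a rank test, and step 5 shows that the comparison can reverse. The questionnaire is not shown and section 3.1 gives no shares of item formats, so nobody can say from the protocol that most items are ordered. The coding of setting and scope is not shown either. All of this stands, and it limits the size of the point. It does not supply the missing rule for nominal-by-ordered pairs.

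**No formal testing is intended.** Section 11.1 says so, but it argues from the descriptive primary objective. For secondary objective 1, section 11.3 prescribes tests and a p-value adjustment, so the choice of test matters there.

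**A stronger reading: unadjusted testing leaves the characteristics confounded, so a multivariable model should be the main analysis.** The protocol does not support this as an error. The stated aim is whether characteristics are associated with implementation, and bivariate tests validly answer that. A simulation with an age effect, no direct sex effect and correlated age and sex shows the unadjusted sex test rejecting in 8% to 99.5% of runs, against 4% to 6% after age adjustment. In those data, however, sex really is marginally associated with the item, so these are not false positives for the stated question. An adjusted model is also something that a statistical analysis plan may add.

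**A further inference: the design variables are neglected.** Region is already one of the tested characteristics, and section 4 samples regions in proportion to membership. The pediatric oversample is small: 2.7% of 825 is about 22 dentists, against a minimum of 50, so roughly 28 extra, or 28/825 ≈ 3% of the sample. An association with patient age that runs through pediatric dentists is a real association.

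**Conclusion.** The point holds as a gap in the choice of test for one kind of pair in a secondary analysis. Section 11.3 names no order-using test for a nominal characteristic against an ordered or percentage item, or against a summary score. If Fisher's Exact Test is applied to 5-level items, the cost is about 17 to 21 percentage points of power at odds ratios 1.3 to 1.5 (n=825, 65/35 split). In the other layouts of step 3 it ranges from about 14 points (50 vs 775, OR 2.5) to about 27 (six graded groups).

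These figures rest on assumed response distributions, group sizes and proportional-odds shifts, at an unadjusted 5% level. Their direction and rough size are the result, not the exact values. The loss applies to ordered items and monotone differences only. The protocol does not support saying that all the responses are ordinal, or that the unadjusted tests are invalid for the stated aim.

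**What to change.** Amend the sentence in section 11.3 so that the test depends on the pair of variables:

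- **Nominal characteristic against an ordered item, a percentage item or a summary score:** Wilcoxon rank-sum for two groups, Kruskal-Wallis for more.
- **Nominal characteristic against a dichotomous or nominal item:** Fisher's Exact Test, as now.
- **Ordinal or interval/ratio pairs:** Spearman and Pearson correlations, as now.

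The cost is a wording change and standard code, with no new data. The small downside is lower sensitivity to non-monotone differences. The frequency tables already planned, shown by characteristic, would still reveal those.

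Optionally, add a multivariable ordinal model (or a linear one for summary scores) as a supportive analysis, to describe which associations persist after adjustment. It should avoid redundant terms: practice scope, pediatric specialty and patient age largely overlap, and there may be only about 50 pediatric dentists. The proportional-odds assumption would also need checking.

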11 STATISTICAL CONSIDERATIONS

11.1 Study Hypotheses

The primary objective of this study is to conduct a national survey of dentists to assess knowledge and behavior related to substance use screening practices. As such, formal hypothesis testing will not be conducted to achieve the study objectives.

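### In secondary objective (1), false-discovery control is tied to the item-level route only, so tests on summary scores have no stated correction

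*Protocol*

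**What the plan says.** Section 11.3 of the Protocol sets out the analysis for secondary objective (1), which asks whether practitioner and practice characteristics go with implementation of screening, counseling and referral.

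- **Tests:** "we will use Fisher's Exact Test for nominal variables and Spearman and Pearson correlations for ordinal and interval/ratio level variables, respectively".
- **Characteristics:** three practitioner characteristics are named (age, sex, race), and the practice characteristics are listed as "including setting, practice scope, practice region, practice patient age, practice patient race, and number of patients per week". Both lists open with the word including, so nine is a minimum.
- **Data reduction:** because there are many items, the team will look into condensing them into scores, by principal components or principal-axis factoring for example. The number of scores is not given, nor is a criterion for when the data support them.
- **Multiplicity:** "If the data do not support the use of summary scores, we will use the Benjamini–Hochberg procedure". This is the only correction in the section, and it applies to one of the two routes.

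Section 11.1, after restating the primary objective, says that "formal hypothesis testing will not be conducted to achieve the study objectives".

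**The concern.** The plan recognises that objective (1) produces multiple tests and names a remedy, then attaches the remedy to one branch. Data reduction cuts the number of tests but does not bring it to one: every retained score is still set against nine or more characteristics. An analyst following the text literally would adjust item-level p-values and leave score-level p-values unadjusted.

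The branch is also chosen after data collection, with no stated criterion. Whether any correction applies to this objective therefore depends on a judgement made with the data in hand.

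At stake is the list of practitioner and practice correlates. The Protocol Summary says the survey is to show whether implementation gaps vary by these characteristics and to inform training and interventions. One or more chance associations in that list could be read as real targets.

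**Working it through.** **The plan's own figures.** The protocol gives no error rate for these analyses, so there is none to reproduce. The only numerical claims in Section 11 concern precision at N = 825. The interval for a mean does reproduce: 1.96/√825 = 0.068 standard deviation units either side. It has no bearing on multiplicity.

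**Inputs**

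- Characteristics, from Section 11.3: 3 practitioner + 6 practice = 9, a minimum.
- Number of summary scores k: not stated, so taken over a range. One is the smallest possible. Three would match screening, counseling and referral. Six would match those three held separately for adolescent and adult patients, since Section 11.3 reports the frequency questions separately for the two groups.
- Significance level: not stated; 0.05 per test assumed.
- Independent tests and all null hypotheses true: assumed.

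**Formulas.** Number of tests m = 9 × k. Chance of at least one false positive = 1 − 0.95^m. Expected false positives = 0.05 × m.

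| Scores k | Tests m | Chance of at least one false positive | Expected false positives |
|---|---|---|---|
| 1 | 9 | 1 − 0.95^9 = 0.370 | 0.45 |
| 2 | 18 | 1 − 0.95^18 = 0.603 | 0.90 |
| 3 | 27 | 1 − 0.95^27 = 0.750 | 1.35 |
| 6 | 54 | 1 − 0.95^54 = 0.937 | 2.70 |

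**Effect of correlation.** Scores from the same dentists are likely to be correlated. With three scores, an assumed pairwise correlation of 0.7 between their test statistics, and the nine characteristics still treated as independent, simulation gives about 65% instead of 75%. The expected number of false positives does not change with correlation, because it is a sum of per-test rates; false positives simply tend to occur together.

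**With the correction on both routes.** If Benjamini-Hochberg at 0.05 were applied to the objective (1) family, the chance of any false positive when all nulls are true and tests are independent would be at most 0.05, whatever the value of k.

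**The case against.** The strongest reply has four parts.

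1. **Summary scores are themselves a response to multiplicity.** This is true, and the protocol introduces them because of the number of items. But the reduction is partial: even one score leaves nine tests.

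2. **The choice of route is not driven by significance.** This also stands. Principal components and factor analysis look at correlations among items, not at their associations with dentist or practice characteristics. A reader might infer from the conditional wording that the team could pick the route giving more significant results. The text does not support that. It says only that the choice depends on the data and has no stated criterion.

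3. **The analyses are secondary in a descriptive survey.** The sample size rests on interval width, and no efficacy or safety conclusion depends on these p-values. This limits the severity and rules out treating the point as a barrier to the study. It does not explain why one branch is corrected and the other is not.

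4. **The larger error rates depend on an assumed number of scores.** Agreed, which is why the range starts at one score. An expectation of several chance associations fits only the 54-test case; with one to three scores the expectation is between 0.45 and 1.35.

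Two stronger readings are tempting but do not hold.

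- **The four adolescent-versus-adult comparisons.** A reader might infer that these, under objective (2), are also planned without correction, since the text says only "We will use paired-sample t-tests to account for the same participant providing both ratings on the adolescents and adults" and adds a Wilcoxon sensitivity analysis. That rests on silence. The Benjamini-Hochberg sentence belongs to objective (1) and neither grants nor denies a correction for objective (2). A statistical analysis plan that is not shown may supply one.
- **Section 11.1.** A reader might infer that it forbids the tests in Section 11.3. Its sentence follows directly from a statement about the primary objective. The unrestricted reference to the study objectives is loose wording and changes no analysis.

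**Conclusion.** The point holds for secondary objective (1), at minor to moderate weight. As written, false-discovery control applies only when summary scores are not used, and the score route leaves at least nine tests per score with no stated correction. This differs from a detail merely left to a later document, because the protocol itself sets the condition and a later plan that corrected both routes would have to go beyond it.

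The chance of at least one false positive runs from 37% (one score) to 94% (six scores). These figures rest on a 0.05 level and a number of scores that the protocol does not state, on independent tests, and on every null being true. Correlation among scores or among characteristics brings the probabilities down. The descriptive primary analysis is unaffected.

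**What to change.** In Section 11.3, secondary objective (1), replace the conditional sentence with: *The Benjamini-Hochberg procedure will be applied to the p-values for secondary objective (1), whether the outcomes are individual items or summary scores.*

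This costs one sentence and needs no extra data, staff or participants. The downside is that some borderline associations will no longer be called significant.

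Editorial note only: limit the Section 11.1 sentence on formal hypothesis testing to the primary objective, since Section 11.3 plans tests for the secondary objectives.
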